6.4.2 BLOOD DONATION

Patients should not donate blood while participating in this study or for at least 90 days following the last infusion of durvalumab or AVB-S6-500.

6.4.3 CONCOMITANT TREATMENT(S)

Investigators may prescribe concomitant medications or treatments (e.g., acetaminophen, diphenhydramine) deemed necessary, as briefly listed in **Table 3**, to provide adequate prophylactic or supportive care except for those medications identified as “excluded” as listed in Table 4. The Principal Investigator must be informed as soon as possible about any medication taken from the time of screening until the end of the clinical phase of the study (final study visit). Any concomitant medication(s), including herbal preparations, taken during the study will be recorded in the medical record.

Table 4. Permitted Supportive Medications

Supportive medication/class of drug:	Usage:
Concomitant medications or treatments (e.g., acetaminophen or diphenhydramine) deemed necessary to provide adequate prophylactic or supportive care, except for those medications identified as “prohibited,” as listed above	To be administered as prescribed by the Investigator or alternate treating physician in consultation with Investigator
Best supportive care (including antibiotics, nutritional support, correction of metabolic disorders, optimal symptom control, and pain management [including palliative radiotherapy to non-target lesions, etc])	Should be used, when necessary, for all patients
Inactivated viruses, such as those in the influenza vaccine	Permitted

Table 5. Prohibited Concomitant Medications

Prohibited medication/class of drug:	Usage:
Any investigational anticancer therapy other than those under investigation in this study	Should not be given concomitantly whilst the patient is on study treatment
mAbs against CTLA-4, PD-1, or PD-L1 other than those under investigation in this study	Should not be given concomitantly whilst the patient is on study treatment
Any concurrent chemotherapy, radiotherapy, immunotherapy, or biologic or hormonal therapy for cancer treatment other than those under investigation in this study	Should not be given concomitantly whilst the patient is on study treatment. (Concurrent use of hormones for non-cancer-related conditions [e.g., insulin for diabetes and hormone replacement therapy] is acceptable. Local treatment of isolated lesions, excluding target lesions, for palliative intent is acceptable [e.g., by local surgery or radiotherapy])

Prohibited medication/class of drug:	Usage:
Immunosuppressive medications including, but not limited to, systemic corticosteroids at doses exceeding 10 mg/day of prednisone or equivalent, methotrexate, azathioprine, and tumor necrosis factor- α blockers	
Should not be given concomitantly or used for premedication prior to the I-O infusions. The following are allowed exceptions:
 
• Use of immunosuppressive medications for the management of IP-related AEs,• Use in patients with contrast allergies.• In addition, use of inhaled, topical, and intranasal corticosteroids is permitted. 
A temporary period of steroids will be allowed if clinically indicated and considered to be essential for the management of non-immunotherapy related events experienced by the patient (e.g., chronic obstructive pulmonary disease, radiation, nausea, etc).

Drugs with laxative properties and herbal or natural remedies for constipation	Should be used with caution through to 90 days after the last dose of durvalumab during the study
EGFR TKIs	Should not be given concomitantly. Should be used with caution in the 90 days post last dose of durvalumab. Increased incidences of pneumonitis (with third generation EGFR TKIs) and increased incidence of transaminase increases (with 1 st generation EGFR TKIs) has been reported when durvalumab has been given concomitantly.
Live attenuated vaccines	Should not be given through 90 days after the last dose of IP (including SoC)
Herbal and natural remedies which may have immune-modulating effects	Should not be given concomitantly unless agreed by Aravive and AstraZeneca

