5.2.2 PRODUCT PREPARATION AND DOSE ADMINISTRATION

Parenteral drug products should be inspected visually for particulate matter and discoloration prior to administration, whenever solution and container permit. AVB-S6-500 should be diluted in normal saline to a total volume of 150 mL (to achieve the desired dose in mg/kg) and administered as an i.v. infusion over 60 minutes.

During combination treatment, durvalumab will be administered prior to AVB-S6-500. IV line flushing in between IP treatments will be performed per institutional policy.

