5.2.3 PRE-MEDICATION FOR AVB-S6-500 DOSING

All patients must be premedicated with anti-H1 and anti-H2 prior to first administration of AVB-S6-500 (Cycle 0 in the AVB-S6-500 monotherapy group; Cycle 1 in the Safety Lead-In and durvalumab monotherapy groups) to reduce the risk and severity of infusion reaction.

Premedication (or components thereof) could be optionally omitted for future cycles, if no infusion reaction was observed during or after the first AVB-S6-500 infusion.

Steroids can be optionally included at the discretion of the treating physician, ideally administered the evening before and again the morning of dosing (for example, dexamethasone 12 mg PO the evening prior and 12 mg PO in the morning prior to dosing). If IV steroids are utilized on the morning of dosing, they should be administered at least 1 hour prior to dosing.

Most infusion reactions occur toward the end of the infusion, or after the infusion has been completed, and patients must be observed for at least 45 minutes after their first AVB-S6-500 infusion.

Any patient who experiences a reaction DURING the infusion and is deemed by the Investigator to be acceptable for same day rechallenge, should be premedicated prior to rechallenge, and the remainder of the infusion should be administered at one-half of the previous infusion rate.

Any patient who experiences a reaction AFTER the infusion and is deemed by the Investigator to be acceptable for rechallenge with the next dose, should be premedicated with an anti-H1, anti-H2, and steroid-containing regimen prior to rechallenge, and the duration of AVB-S6-500 at rechallenge should be 2 hours (instead of 1 hour).

If the patient tolerates AVB-S6-500 upon rechallenge, the premedication regimen and infusion duration should remain the same for subsequent dosing.

Infusion reactions should be managed symptomatically. Meperidine should be considered for treatment of rigors.

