^o Resting 12-lead ECG on which QTcF must be < 470 ms. ECGs should be obtained after the patient has been in a supine position for 5 minutes and recorded while the patient remains in that position. In case of clinically significant ECG abnormalities, including a QTcF value > 470 ms, 2 additional 12-lead ECGs should be obtained over a brief period (e.g., 30 minutes) to confirm the finding. ECGs may be performed more frequently than noted in the schedule if clinically indicated.

^p Imaging to occur Q8W (± 7 days) and should continue unless the subject has confirmed progression, death or unacceptable toxicity. If progression is identified, then a confirmatory scan should be obtained 6 weeks (± 7 days) after the first positive scan. As long as treatment is being well-tolerated and the investigator believes that the patient may derive benefit, the patient should continue regularly scheduled visits and receive additional treatment until the confirmatory scan results have been reviewed.

^q Patients with suspected brain metastases at screening should have an MRI (preferred) or CT each preferably with intravenous (IV) contrast of the brain.

^r To occur during the final week of the marked Cycle, prior to initiating treatment in the following Cycle.

^s RECIST measurements will be performed in line with imaging. Refer to **Section 7.1**.

^t Refer to **Section 6.6.2** for details regarding Tumor sample.

^u Biopsy can be newly acquired or archival ≤ 3 years old. Refer to **Section 6.6.2** for details regarding tumor sample.

^v If subjects are not required to have a diagnostic biopsy (i.e. tumor recurrence/progression has been already histologically confirmed), tissue acquisition will occur during a research-only biopsy procedure. Refer to **Section 6.6.2** for details regarding tumor sample.

^w To occur immediately prior to Cycle 3 where possible. Refer to **Section 6.6.2** for details regarding tumor sample.

^x Sample will be taken within 45 minutes before dosing. Additional post-dose time points will be collected only on Day 1 of Cycle 1. See note “y” below. Refer to **Section 6.6.1**. A blood sample will be collected and processed for serum at the 90-day follow up visit to analyze for the presence of anti-drug antibodies for AVB-S6-500.

^y Samples will be taken within 45 minutes before dosing begins and at 1 and 4 hours after the completion of treatment. Refer to **Section 6.6.1**.

^z Cycles 3 and 4 only.

^{aa} Refer to **Section 5.2**.

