		
 – Acetaminophen and/or antihistamines may be administered per institutional standard at the discretion of the investigator. – Consider premedication per institutional standard prior to subsequent doses.
	For Grade 2 The infusion rate of study drug/study regimen may be decreased 50% or temporarily interrupted until resolution of the event. Subsequent infusions may be given at 50% of the initial infusion rate.	
 – Steroids should not be used for routine premedication of Grade ≤ 2 infusion reactions.
Grade 3 or 4	For Grade 3 or 4 Permanently discontinue study drug/study regimen.	For Grade 3 or 4
		
 – Manage severe infusion-related reactions per institutional standards (e.g., IM epinephrine, followed by IV diphenhydramine and famotidine, and IV glucocorticoid).
		CTCAE Common Terminology Criteria for Adverse Events; IM intramuscular; IV intravenous; NCI National Cancer Institute.

Table 20. Non-immune-mediated Reactions

Severity Grade of the Event (Refer to NCI CTCAE applicable version in study protocol for defining the CTC grade/severity)	Dose Modifications	Toxicity Management
Any Grade	Note: Dose modifications are not required for AEs not deemed to be related to study treatment (i.e., events due to underlying disease) or for laboratory abnormalities not deemed to be clinically significant.	Treat accordingly, as per institutional standard.
Grade 1	No dose modifications.	Treat accordingly, as per institutional standard.
Grade 2	Hold study drug/study regimen until resolution to \leq Grade 1 or baseline.	Treat accordingly, as per institutional standard.
Grade 3	Hold study drug/study regimen until resolution to \leq Grade 1 or baseline. For AEs that downgrade to \leq Grade 2 within 7 days or resolve to \leq Grade 1 or baseline within 14 days, resume study drug/study regimen administration. Otherwise, discontinue study drug/study regimen.	Treat accordingly, as per institutional standard.
Grade 4	Discontinue study drug/study regimen (Note: For Grade 4 labs, decision to discontinue should be based on accompanying clinical signs/symptoms, the Investigator's clinical judgment, and consultation with the MDACC IND Office and supporting companies.).	Treat accordingly, as per institutional standard.

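### Section 5.2.3 permits optional steroid premedication that Table 5 prohibits before durvalumab, so some plasma/PBMC samples, notably the lead-in baseline, may follow steroid exposure in some patients only

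*Combined protocol and SAP*

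**What the plan says.** Three current sections deal with steroid premedication.

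- **Section 5.2.3** makes anti-H1 and anti-H2 premedication mandatory before the first AVB-S6-500 dose and leaves steroids open: "Steroids can be optionally included at the discretion of the treating physician, ideally administered the evening before and again the morning of dosing". Its example is "dexamethasone 12 mg PO the evening prior and 12 mg PO in the morning prior to dosing". A patient who reacts after the infusion and is judged fit for rechallenge "should be premedicated with an anti-H1, anti-H2, and steroid-containing regimen prior to rechallenge". If the first infusion causes no reaction, premedication or parts of it may be dropped later.
- **Table 5 (Section 6.4.3)** lists immunosuppressives, including systemic corticosteroids above 10 mg/day prednisone equivalent, and says: "Should not be given concomitantly or used for premedication prior to the I-O infusions". The exceptions are management of AEs related to investigational product, contrast allergy, inhaled, topical or intranasal use, and temporary steroids essential for managing non-immunotherapy events.
- **Appendix A, Table 19**, in guidelines covering both drugs, says: "Steroids should not be used for routine premedication of Grade" 2 or lower infusion reactions. For Grade 3 or 4 it stops treatment permanently.

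On infusion order, Section 5.2.2 says: "During combination treatment, durvalumab will be administered prior to AVB-S6-500". Table 6 schedules both drugs on Day 1 of every lead-in cycle. On research blood, Table 6 footnote x says: "Sample will be taken within 45 minutes before dosing".

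**The concern.** A physician who uses the Section 5.2.3 option on a durvalumab day departs from Table 5, and one who follows Table 5 cannot use the option as exemplified. With no statement of precedence, patients in the same cohort may be premedicated differently under one protocol.

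For the data, the issue is what a pre-dose sample represents. If some patients have taken a systemic immunosuppressive steroid before the baseline draw and others have not, baseline immune profiles are not comparable between patients. Because premedication can be dropped after an uneventful first infusion, a patient may also be exposed at baseline and unexposed later. A change from baseline in a blood immune marker could then partly reflect steroid withdrawal.

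**Working it through.** No power, alpha or sample-size figure is involved. The check sets the passages side by side, with two small calculations.

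**1. Does the example dose fall within the Table 5 row?** The threshold is 10 mg/day prednisone equivalent. One 12 mg dexamethasone dose exceeds it at any conversion factor above 10/12 = 0.83 mg prednisone per mg dexamethasone. The documents give no factor. Assuming 5 to 7.5, one dose is 12 × 5 = 60 mg to 12 × 7.5 = 90 mg. Each dose alone is over the limit, so splitting them across two calendar days makes no difference.

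**2. Do the steroids precede an immunotherapy infusion?** On Day 1 durvalumab goes in before AVB-S6-500. A steroid taken the evening before AVB-S6-500 therefore also precedes durvalumab, and so does a morning dose taken before the first infusion. Table 5 does not define "I-O". If it means durvalumab only, the premedication clause applies on Day 1 and not to the AVB-S6-500-only infusion on Day 15. All the scheduled plasma/PBMC draws in Table 9 are on Day 1.

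**3. Does an exception apply?**

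| Use under Section 5.2.3 | Table 5 | Appendix A, Table 19 |
|---|---|---|
| Optional prophylaxis, no prior reaction | Prohibited; there is no AE to manage, no contrast allergy and no event experienced | Does not address a patient without a reaction |
| Rechallenge after a post-infusion reaction | Arguably covered by the exception for managing product-related AEs | Advises against routine steroid premedication at Grade 2 or lower |

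Because Table 19 stops treatment at Grade 3 or 4, rechallenge mainly concerns the Grade 2 or lower group. Exclusion criterion 16c exempts steroid premedication at entry; it does not govern on-study use.

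**4. Can a research sample follow the steroid?** Blood is drawn no more than 45 minutes before dosing, so an evening-before dose always precedes it. For IV steroids Section 5.2.3 says "they should be administered at least 1 hour prior to dosing". If that hour is counted to the first infusion of the day, the steroid precedes the blood by at least 60 − 45 = 15 minutes. If it is counted to AVB-S6-500, which follows a standard 1-hour durvalumab infusion, an IV steroid could come after the draw. The oral example does not depend on this reading.

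**5. Which samples matter?** In the lead-in, Table 9 has no Cycle 0 sample, so Cycle 1 Day 1 is the only scheduled pre-treatment plasma/PBMC draw. Section 5.2.3 places the first premedication at that same dose. Further plasma/PBMC draws fall on Day 1 of Cycles 2, 3 and 4. A lead-in patient can therefore have from 0 to 4 exposed samples.

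**6. What do they feed?** Section 6.6.1 assigns plasma and PBMCs to gene expression, functional proteomics and immune profiling. Section 9.2 contains no flag, stratification or sensitivity summary for steroid exposure.

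**The case against.** Much can be said for a narrower reading, and most of it stands.

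- A reader might infer that Section 5.2.3 *requires* what Table 5 forbids. Steroids are directed only at rechallenge after a post-infusion reaction, and Table 5's exception for product-related AEs arguably covers that use. The remaining tension there is with Appendix A, and it is soft: the advice concerns routine use, and the guidelines are offered in support of clinical judgment.
- A reader might infer that secondary objective 3 is confounded. Section 9.2 compares T-cell populations between pre- and post-treatment biopsies, with similar summaries for macrophage phenotypes. Pre-treatment tissue is taken at screening or is archival, not in the 45 minutes before dosing. Steroid timing relative to biopsy has not been shown to be a problem.
- A reader might infer that all Day 1 research blood is affected. Serum goes to AVB-S6-500 concentration, GAS6 and anti-drug antibodies, for which no steroid effect is argued, and premedication may lapse after the first infusion.
- A reader might see a flaw in the DLT definition, because Section 6.2 excludes a first Grade 3 infusion reaction resolving within 6 hours only without steroid prophylaxis. That text anticipates prophylaxis, and a Grade 3 non-immune event that resolves within hours may not meet the listed DLT criteria anyway. No effect on dose decisions is shown.
- Differing management is possible, not certain: recruitment is from one department at one centre, and enrollment ended after the fifth evaluable subject (Section 3.1).

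None of this removes the conflict over optional prophylaxis on a durvalumab day, or the possibility of a steroid-exposed baseline PBMC sample.

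**Conclusion.** The contradiction between Section 5.2.3 and Table 5 holds for optional prophylactic steroids given before a Day 1 combination infusion to a patient with no prior reaction. It does not depend on the dexamethasone conversion factor for any value above 0.83, or on whether the immunotherapy infusions in Table 5 include AVB-S6-500. The tension between the rechallenge regimen and Appendix A is real but weaker.

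For the data, plasma/PBMC correlates, especially the lead-in baseline at Cycle 1 Day 1, may be drawn after steroid exposure in some patients only, and the plan has no step to detect this. The size cannot be stated: the documents do not say whether any patient received optional steroids, so the number could be none or all of those treated. With so few patients, even one exposed baseline could matter to a descriptive summary of the blood correlates.

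**What to change.** 1. Reconcile Section 5.2.3, Table 5 and Appendix A (Table 19) to one rule on steroid premedication, covering optional prophylaxis and rechallenge, and define the immunotherapy infusions to which Table 5 refers. Which clinical rule applies is the sponsor's decision.
2. From the concomitant-medication records, list systemic steroid exposure before each plasma/PBMC sample, with dose and time where available, and flag exposed samples.
3. Add to Section 9.2 a summary of the blood correlates with and without the flagged samples, marking patients whose baseline is exposed.

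The cost is a wording amendment, one listing and one extra descriptive summary. Section 6.4.3 and Table 6 already require concomitant medications to be recorded. They do not ask explicitly for the time of each dose, so the evening-before dose may have to be taken from source notes. With enrollment closed, the wording change can affect only continuing treatment; the listing and flag serve the samples already collected.

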6.5 SCHEDULES OF STUDY ASSESSMENTS AND PROCEDURES

Table 6. Schedule of Assessments and Procedures: Safety Lead-in

	Screening 1	Screening 2	Cycle 1 (4 weeks)		Cycle 2 (4 weeks)		Cycle 3+ ^a (4 weeks)		EOT ^b	Follow-up ^c	
			Day 1	Day 15	Day 1	Day 15	Day 1	Day 15		30 Days	90 Days
Assessment/Procedure	Days -28 to -1	Days -28 to -1	N/A	±7 Days						±3 Days	±7 Days
Written Informed Consent	X ^d										
Medical History	X										
Physical Exam ^e	X		X	X	X	X	X	X	X	X	X
Vital Signs ^f	X		X ^g	X	X	X	X	X	X	X	X
ECOG PS	X		X	X	X	X	X	X	X	X	X
Adverse Event Evaluation	X		X	X	X	X	X	X	X	X	X
Concomitant medications	X		X	X	X	X	X	X	X	X	X
CBC w/Diff ^h	X		X	X	X	X	X	X	X	X	X
Chemistry Panel ⁱ	X		X	X	X	X	X	X	X	X	X
Beta hCG ^j	X		X		X		X		X		
Thyroid Function ^k	X		X		X		X		X		
Urinalysis ^l	X		X		X		X		X	X	X
Coagulation ^m	X										
Hepatitis/HIV Screening ⁿ	X										
ECG ^o	X										
Tumor Imaging ^p	X ^q					X ^r					
RECIST ^s	X					X					
Biopsy ^t	X ^u	X ^v				X ^w					
CA125			X		X		X		X		
Research Blood ^x			X ^y		X		X ^z				X
AVB-S6-500 dosing ^{aa}			X	X	X	X	X	X			
Durvalumab dosing ^{bb}			X		X		X				

^a The procedures/assessments including treatment will continue until intolerable toxicity or confirmed progression.

^b End of treatment (EOT) is defined as the last visit where the decision is made to discontinue protocol directed treatment, including confirmed progression of disease. All required procedure may be completed within ± 7 days of the end of treatment visit. Repeat disease assessment is not required if performed within 35 days prior to the EOT visit.

^c For subjects who end treatment due to progression, follow-up visits will occur every 6 weeks for at least 90 days or until initiation of subsequent treatment or alternative trial. For subjects who are no longer receiving study drug(s) but have not had confirmed progression, follow-up with clinical and laboratory evaluation will occur every 6 weeks with imaging assessment every 12 weeks (unless more frequent assessment is clinically indicated) for at least 90 days or until progression, whichever occurs later. All patients should have further chemistry profiles performed at 30 days (±3 days) and 90 days (±1 week) after permanent discontinuation of IP. All patients will be followed for survival. Patients who decline to return to the site for evaluations will be offered follow-up by phone every 6 months as an alternative.

^d Informed consent of study procedures and pretreatment tumor biopsy sample may be obtained prior to the 28-day screening window, if necessary, in order to permit tumor biopsy sample acquisition and analysis prior to randomization. If laboratory or imaging procedures were performed for alternate reasons prior to signing consent,

these can be used for screening purposes with consent of the patient. However, all screening laboratory and imaging results must have been obtained within 28 days of randomization.

^e Full physical exam will be performed at screening, with targeted physical exam at all other time points. Body weight is recorded at each visit. Height to be performed at screening only.

^f Routine vital signs to be performed at each visit, and these should occur prior to infusion on treatment days. On treatment days, BP and pulse will be collected from patients prior to the beginning of the infusion (measured once from approximately 30 minutes before up to 0 minutes [i.e., the beginning of the infusion]), approximately 30 minutes during the infusion (halfway through infusion), and at the end of the infusion (approximately 60 minutes \pm 5 minutes). If the infusion takes longer than 60 minutes, then BP and pulse measurements should follow the principles as described above or be taken more frequently if clinically indicated.

^g A 1-hour observation period is recommended after the first dose of combination therapy.

^h May be performed more frequently than noted in the schedule if clinically indicated. CBC with differential includes: basophils, eosinophils, hematocrit, hemoglobin, lymphocytes, mean corpuscular hemoglobin, mean corpuscular hemoglobin concentration, mean corpuscular volume, monocytes, neutrophils, platelet count, red blood cell count, and total white cell count.

ⁱ May be performed more frequently than noted in the schedule if clinically indicated. Chemistry Panel includes: albumin, alkaline phosphatase, alanine aminotransferase, amylase, aspartate aminotransferase, bicarbonate, calcium, chloride, creatinine, gamma glutamyltransferase, glucose, lactate dehydrogenase, lipase, magnesium, potassium, sodium, total bilirubin total protein, BUN, and uric acid. If total bilirubin is $\geq 2 \times$ ULN (and no evidence of Gilbert's syndrome) then fractionate into direct and indirect bilirubin. Amylase and lipase are to be performed at screening, Day 1 of each cycle, and at EOT. It is preferable that both amylase and lipase parameters are assessed. For sites where only 1 of these parameters is routinely measured then either lipase or amylase is acceptable. Bicarbonate, chloride, creatinine clearance, and magnesium testing are to be performed at screening, on Day 0 (if required), and if clinically indicated. If a patient shows an AST or ALT $\geq 3 \times$ ULN together with total bilirubin $\geq 2 \times$ ULN, refer to **Section 6.3** for further instructions on cases of increases in liver biochemistry and evaluation of Hy's Law. Gamma glutamyltransferase may be included at any time if clinically indicated.

^j Serum B-HCG within 72 hours prior to the first dose of therapy and as clinically indicated prior to day 1 of each subsequent cycle and at end of treatment only in women of childbearing potential (women who are not surgically-sterile or post-menopausal).

^k Free T3 or free T4 will only be measured if TSH is abnormal or if there is a clinical suspicion of an AE related to the endocrine system.

^l Urinalysis includes: bilirubin, blood, glucose, ketones, pH, protein, specific gravity, color, and appearance. Microscopy should be used as appropriate to investigate white blood cells and use the high-power field for red blood cells

^m May be performed more frequently than noted in the schedule if clinically indicated. Coagulation testing includes: PT, aPTT, and INR.

ⁿ Hepatitis screening tests include: HCV-Ab, HBsAg, HBcAb, and HBsAb.

^o Resting 12-lead ECG on which QTcF must be < 470 ms. ECGs should be obtained after the patient has been in a supine position for 5 minutes and recorded while the patient remains in that position. In case of clinically significant ECG abnormalities, including a QTcF value > 470 ms, 2 additional 12-lead ECGs should be obtained over a brief period (e.g., 30 minutes) to confirm the finding. ECGs may be performed more frequently than noted in the schedule if clinically indicated.

^p Imaging to occur Q8W (± 7 days) and should continue unless the subject has confirmed progression, death or unacceptable toxicity. If progression is identified, then a confirmatory scan should be obtained 6 weeks (± 7 days) after the first positive scan. As long as treatment is being well-tolerated and the investigator believes that the patient may derive benefit, the patient should continue regularly scheduled visits and receive additional treatment until the confirmatory scan results have been reviewed.

^q Patients with suspected brain metastases at screening should have an MRI (preferred) or CT each preferably with intravenous (IV) contrast of the brain.

^r To occur during the final week of the marked Cycle, prior to initiating treatment in the following Cycle.

^s RECIST measurements will be performed in line with imaging. Refer to **Section 7.1**.

^t Refer to **Section 6.6.2** for details regarding Tumor sample.

^u Biopsy can be newly acquired or archival ≤ 3 years old. Refer to **Section 6.6.2** for details regarding tumor sample.

^v If subjects are not required to have a diagnostic biopsy (i.e. tumor recurrence/progression has been already histologically confirmed), tissue acquisition will occur during a research-only biopsy procedure. Refer to **Section 6.6.2** for details regarding tumor sample.

^w To occur immediately prior to Cycle 3 where possible. Refer to **Section 6.6.2** for details regarding tumor sample.

^x Sample will be taken within 45 minutes before dosing. Additional post-dose time points will be collected only on Day 1 of Cycle 1. See note “y” below. Refer to **Section 6.6.1**. A blood sample will be collected and processed for serum at the 90-day follow up visit to analyze for the presence of anti-drug antibodies for AVB-S6-500.

^y Samples will be taken within 45 minutes before dosing begins and at 1 and 4 hours after the completion of treatment. Refer to **Section 6.6.1**.

^z Cycles 3 and 4 only.

^{aa} Refer to **Section 5.2**.

^{bb} Refer to **Section 5.1**.

Table 7. Schedule of Assessments and Procedures: Phase II, Durvalumab Monotherapy Cohort

	Screening 1	Screening 2	Cycle 0 (6 Weeks)			Cycle 1 (4 Weeks)		Cycle 2 (4 Weeks)		Cycle 3+ ^a (4 Weeks)		EOT ^b	Follow-up ^c	
			Day 1	Day 22	Day 29	Day 1	Day 15	Day 1	Day 15	Day 1	Day 15		30 Days	90 Days
Assessment/Procedure	Days -28 to -1	Days -28 to -1	N/A	±7 Days									±3 Days	±7 Days
Written Informed Consent	X ^d													
Medical History	X													
Physical Exam ^e	X		X	X		X	X	X	X	X	X	X	X	X
Vital Signs ^f	X		X ^g	X		X ^h	X	X	X	X	X	X	X	X
ECOG PS	X		X	X		X	X	X	X	X	X	X	X	X
Adverse Event Evaluation	X		X	X		X	X	X	X	X	X	X	X	X
Concomitant medications	X		X	X		X	X	X	X	X	X	X	X	X
CBC w/Diff ⁱ	X		X	X		X	X	X	X	X	X	X	X	X
Chemistry Panel ^j	X		X	X		X	X	X	X	X	X	X	X	X
Beta hCG ^k	X		X			X		X		X		X		
Thyroid Function ^l	X					X		X		X		X		
Urinalysis ^m	X		X			X		X		X		X	X	X
Coagulation ⁿ	X													
Hepatitis/HIV Screening ^o	X													
ECG ^p	X													
Tumor Imaging ^q	X ^r				X ^s				X ^s					
RECIST ^t	X				X				X					
Biopsy ^u	X ^v	X ^w			X ^x				X ^y					
CA125			X			X		X		X		X		
Research Blood ^z			X			X		X		X ^{aa}				X
AVB-S6-500 dosing ^{bb}						X	X	X	X	X	X			
Durvalumab dosing ^{cc}			X	X		X		X		X				

^a The procedures/assessments including treatment will continue until intolerable toxicity or confirmed progression.

^b End of treatment (EOT) is defined as the last visit where the decision is made to discontinue protocol directed treatment, including confirmed progression of disease. All required procedure may be completed within ± 7 days of the end of treatment visit. Repeat disease assessment is not required if performed within 35 days prior to the EOT visit.

^c For subjects who end treatment due to progression, follow-up visits will occur every 6 weeks for at least 90 days or until initiation of subsequent treatment or alternative trial. For subjects who are no longer receiving study drug(s) but have not had confirmed progression, follow-up with clinical and laboratory evaluation will occur every 6 weeks with imaging assessment every 12 weeks (unless more frequent assessment is clinically indicated) for at least 90 days or until progression, whichever occurs later. All patients should have further chemistry profiles performed at 30 days (±3 days) and 90 days (±1 week) after permanent discontinuation of IP. All patients will be followed for survival. Patients who decline to return to the site for evaluations will be offered follow-up by phone every 6 months as an alternative.

^d Informed consent of study procedures and pretreatment tumor biopsy sample may be obtained prior to the 28-day screening window, if necessary, in order to permit tumor biopsy sample acquisition and analysis prior to

randomization. If laboratory or imaging procedures were performed for alternate reasons prior to signing consent, these can be used for screening purposes with consent of the patient. However, all screening laboratory and imaging results must have been obtained within 28 days of randomization.

^c Full physical exam will be performed at screening, with targeted physical exam at all other time points. Body weight is recorded at each visit. Height to be performed at screening only.

^f Routine vital signs at each visit and should occur prior to infusion on treatment days. On treatment days, BP and pulse will be collected from patients prior to the beginning of the infusion (measured once from approximately 30 minutes before up to 0 minutes [i.e., the beginning of the infusion]), approximately 30 minutes during the infusion (halfway through infusion), and at the end of the infusion (approximately 60 minutes \pm 5 minutes). If the infusion takes longer than 60 minutes, then BP and pulse measurements should follow the principles as described above or be taken more frequently if clinically indicated.

^g A 1-hour observation period is recommended after the first infusion of durvalumab.

^h A 1-hour observation period is recommended after the first dose of combination therapy.

ⁱ May be performed more frequently than noted in the schedule if clinically indicated. CBC with differential includes: basophils, eosinophils, hematocrit, hemoglobin, lymphocytes, mean corpuscular hemoglobin, mean corpuscular hemoglobin concentration, mean corpuscular volume, monocytes, neutrophils, platelet count, red blood cell count, and total white cell count.

^j May be performed more frequently than noted in the schedule if clinically indicated. Chemistry Panel includes: albumin, alkaline phosphatase, alanine aminotransferase, amylase, aspartate aminotransferase, bicarbonate, calcium, chloride, creatinine, gamma glutamyltransferase, glucose, lactate dehydrogenase, lipase, magnesium, potassium, sodium, total bilirubin total protein, BUN, and uric acid. If total bilirubin is $\geq 2 \times$ ULN (and no evidence of Gilbert's syndrome) then fractionate into direct and indirect bilirubin. Amylase and lipase are to be performed at screening, Day 1 of each cycle, and at EOT. It is preferable that both amylase and lipase parameters are assessed. For sites where only 1 of these parameters is routinely measured then either lipase or amylase is acceptable. Bicarbonate, chloride, creatinine clearance, and magnesium testing are to be performed at screening, on Day 0 (if required), and if clinically indicated. If a patient shows an AST or ALT $\geq 3 \times$ ULN together with total bilirubin $\geq 2 \times$ ULN, refer to **Section 6.3** for further instructions on cases of increases in liver biochemistry and evaluation of Hy's Law. Gamma glutamyltransferase may be included at any time if clinically indicated.

^k Serum B-HCG within 72 hours prior to the first dose of therapy and as clinically indicated prior to day 1 of each subsequent cycle and at end of treatment only in women of childbearing potential (women who are not surgically-sterile or post-menopausal).

^l Free T3 or free T4 will only be measured if TSH is abnormal or if there is a clinical suspicion of an AE related to the endocrine system.

^m Urinalysis includes: bilirubin, blood, glucose, ketones, pH, protein, specific gravity, color, and appearance. Microscopy should be used as appropriate to investigate white blood cells and use the high-power field for red blood cells.

ⁿ May be performed more frequently than noted in the schedule if clinically indicated. Coagulation testing includes: PT, aPTT, and INR.

^o Hepatitis screening tests include: HCV-Ab, HBsAg, HBcAb, and HBsAb.

^p Resting 12-lead ECG on which QTcF must be < 470 ms. ECGs should be obtained after the patient has been in a supine position for 5 minutes and recorded while the patient remains in that position. In case of clinically significant ECG abnormalities, including a QTcF value > 470 ms, 2 additional 12-lead ECGs should be obtained over a brief period (e.g., 30 minutes) to confirm the finding. ECGs may be performed more frequently than noted in the schedule if clinically indicated.

^q Imaging to occur Q8W (± 7 days) and should continue as long as the subject has not had confirmed progression, death or unacceptable toxicity. If progression is identified, then a confirmatory scan should be obtained 6 weeks (± 7 days) after the first positive scan. As long as treatment is being well-tolerated and the investigator believes patient may derive benefit, the patient should continue regularly scheduled visits and receive additional treatment until the confirmatory scan results have been reviewed.

^r Patients with suspected brain metastases at screening should have an MRI (preferred) or CT each preferably with intravenous (IV) contrast of the brain.

^s To occur during the final week of the marked Cycle, prior to initiating treatment in the following Cycle.

^t RECIST measurements will be performed in line with imaging. Refer to **Section 7.1**.

^u Refer to **Section 6.6.2**.

^v Biopsy can be newly acquired (standard-of-care) or archival ≤ 3 years old. Refer to **Section 6.6.2** for details regarding tumor sample.

^w If subjects are not required to have a diagnostic biopsy (i.e. tumor recurrence/progression has been already histologically confirmed), tissue acquisition will occur during a research-only biopsy procedure. Refer to **Section 6.6.2** for details regarding tumor sample.

^x To occur immediately prior to initiation of combination therapy. Refer to **Section 6.6.2** for details regarding tumor sample.

^y To occur immediately prior to initiation of Cycle 3 where possible. Refer to **Section 6.6.2** for details regarding Tumor sample.

^z Sample will be taken within 45 minutes before dosing. Refer to **Section 6.6.1**. A blood sample will be collected and processed for serum at the 90-day follow up visit to analyze for the presence of anti-drug antibodies for AVB-S6-500.

^{aa} Cycles 3 and 4 only.

^{bb} Refer to **Section 5.2**.

^{cc} Refer to **Section 5.1**.

Table 8. Schedule of Assessments and Procedures: Phase II, AVB-S6-500 Monotherapy Cohort

